Baseline demographic data, psychiatric comorbidities, seizure frequency, quality of life, and healthcare resource utilization will be recorded following enrollment during the inpatient stay as part of PHRC IRB protocol 2013P000133. If the patient is not enrolled in protocol 2013P000133, baseline demographic data, seizure data, psychiatric comorbidities, qualities of life and healthcare resource utilization will be collected during the admission at which the patient is diagnosed, as detailed in appendix 1. All enrolled subjects will be scheduled for an initial appointment in the joint psychiatry-neurology clinic with a board certified neuropsychiatrist and board certified neurologists, which is standard of care for newly diagnosed PNES patients at Brigham and Women’s Hospital.

All subjects will attend the initial clinic visit with the neuropsychiatrist and epileptologist. At the end of this visit, those subjects randomized to motivational interviewing will be questioned using standardized motivational interviewing techniques by the study author who is a board certified neurologist and who will have formal training and certification in motivational interviewing. Motivational interviews will include the classical 4 steps of MI: 1) engagement (in which the patient’s goals and interests are elicited and the therapeutic alliance is established); 2) focusing (in which the specific subjects of discussion and intervention are negotiated); 3) strengthening motivation (in which the patients’ reasons for healthcare intervention are made explicit, discussed, and reinforced); and 4) planning (in which actions for healthcare intervention are planned out based on the patients’ own goals and interests).

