All subjects will be contacted by phone at 4 month follow-up. If necessary they will be called 5 times at various times during the day and early evening. If they are not reached, they will receive a letter requesting them to contact the study staff to complete the study. Subjects will be questioned about their adherence to treatment. The primary outcome will be the number of psychotherapy sessions for the treatment of PNES in which they have participated over the past three months. They will also be assessed for secondary outcomes including dichotomous adherence (either seizure freedom or active participation in psychotherapy for the treatment of PNES, with more than 5 sessions over the past 3 months), seizure frequency over the past month, number of hospitalizations and emergency department visits over the past 3 months, and quality of life as measured by the brief QOLIE-10 instrument. For those patients who give permission, their psychotherapists will be contacted by study staff to confirm the exact number of psychotherapy sessions over the past 3 months. A standard Partners clinical records release form with the patient’s signature will be sent to the therapist’s office.

Biostatistical Analysis:

A) Motivational Interviewing Treatment Integrity

Fidelity to motivational interviewing techniques during motivational interviewing sessions (intervention arm) will be assessed by blinded reviewers using the Motivational Interviewing Treatment Integrity code (MITI) 4.0. Relational scores and technical scores of ≥ 4 will be taken as indicating adherence to motivational interviewing techniques. Conversely abstinence from motivational interviewing techniques during informational interviews (control arm) will also be assessed by blinded reviewers using the MITI 4.0. Relational scores and technical scores of ≤ 2 will be taken as indicating abstinence from motivational interviewing techniques.

B) Outcome data

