Outcome data collected during study, collected at 4 month follow-up, includes seizure frequency over the past 3 months, number of emergency department visits over the past 3 months, QOLIE-10 score (see attached instrument), and participation in psychotherapy for the treatment of PNES (and number of sessions over the past 3 months). The primary outcome will be adherence, defined as attending 8 or more psychotherapy sessions over the past 3 months. Secondary outcomes will include decrease in PNES frequency, seizure freedom, change in QOLIE-10 score, and change in monthly ED visits.

Intergroup comparisons will be made between the treatment arm (motivational interviewing) and control arm (informational interviewing) using the t-test or Wilcoxon rank-sum test depending on normality of distributions.

C) Power analysis:

Sample size of 30-per-arm was calculated to detect a difference in adherence of 25% vs. 60% with power of 0.80 and alpha of 0.05.

For studies involving treatment or diagnosis, provide information about standard of care at Partners (e.g., BWH, MGH) and indicate how the study procedures differ from standard care. Provide information on available alternative treatments, procedures, or methods of diagnosis.

All patients enrolled in study will still receive standard of care for patients diagnosed with PNES at Brigham and Women's Hospital: initial clinical follow-up with neuropsychiatrist and epileptologist and psychotherapy from a licensed therapist. Study patients will additionally receive either an informational interview (control arm) or a motivational interview (treatment arm) following their initial clinic follow-up.

Describe how risks to subjects are minimized, for example, by using procedures which are consistent with sound research design and which do not unnecessarily expose subjects to risk or by using procedures already being performed on the subject for diagnostic or treatment purposes.

Research procedures (motivational interviewing vs. informational interview) are consistent with sound research design. Motivational interviewing has been studied and used for years in promoting abstinence from substance abuse and adherence with treatment in other disorders (HIV, schizophrenia, etc.), and is thought to be associated with minimal risk.

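### The three change-from-baseline secondaries (QOLIE-10, PNES frequency, ED visits) are compared without baseline adjustment, which loses precision that data already collected would supply

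*Combined protocol and SAP*

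**What the plan says.** Under Biostatistical Analysis, B) Outcome data, the plan states: "Secondary outcomes will include decrease in PNES frequency, seizure freedom, change in QOLIE-10 score, and change in monthly ED visits". Three of these four are changes from baseline; seizure freedom is yes/no. The same section compares the arms "using the t-test or Wilcoxon rank-sum test depending on normality of distributions". No regression, ANCOVA or other baseline adjustment appears anywhere in the document.

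Research Design and Methods provides for the baseline values. For patients also in the companion protocol: "Baseline demographic data, psychiatric comorbidities, seizure frequency, quality of life, and healthcare resource utilization will be recorded following enrollment during the inpatient stay". For the others: "seizure data, psychiatric comorbidities, qualities of life and healthcare resource utilization will be collected during the admission at which the patient is diagnosed". An earlier paragraph of that section lists baseline recording ahead of randomization.

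The two descriptions of follow-up differ. The 4-month follow-up paragraph collects "seizure frequency over the past month, number of hospitalizations and emergency department visits over the past 3 months", and QOLIE-10, as values at follow-up. The Outcome data paragraph "includes seizure frequency over the past 3 months" and analyses change. The primary outcome differs too: "The primary outcome will be the number of psychotherapy sessions" in the first place, and "The primary outcome will be adherence, defined as attending 8 or more psychotherapy sessions over the past 3 months" in the second.

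**The concern.** A change score uses baseline only by subtraction, which fixes the slope of follow-up on baseline at 1. When the true slope is below 1, as it is with equal SDs and a correlation below 1, subtraction over-corrects. The estimate stays unbiased over randomizations, but it carries extra noise and passes part of any chance baseline imbalance into the result. ANCOVA estimates the slope from the data.

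A change score also needs the same recall window at both times. The document gives two windows for 4-month seizure frequency (one month and three months) and, in the text available, none at baseline. A baseline covariate needs no matching window.

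Aim 3 and Hypothesis 3 name seizure frequency, healthcare usage and quality of life. The trial is sized only for adherence, so these outcomes have little precision to spare. At stake is a real effect on them being missed, or reported with a wider interval than the data require.

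**Working it through.** **The plan's own figure.** C) Power analysis gives 30 per arm for 25% vs. 60%, power 0.80, alpha 0.05. The two-sided pooled formula, with mean proportion 0.425, is

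n = [1.960·√(2·0.425·0.575) + 0.842·√(0.25·0.75 + 0.60·0.40)]² / 0.35² = 30.1,

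which rounds up to 31. The arcsine formula gives 30, and the approximate power at 30 per arm is 0.7985. The figure reproduces. It concerns yes/no adherence, so this point does not touch it.

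**QOLIE-10.** Inputs: 30 per arm (Research Design and Methods). Assumed: correlation r of 0.3, 0.5 or 0.7, equal SDs at both times, a linear relation and complete data. Per unit outcome variance:

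- change score: 2(1−r)
- ANCOVA: 1−r², times 1 + 1/(60−4) = 1.018 for estimating the slope
- ratio before that cost: (1−r²) / [2(1−r)] = (1+r)/2

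The arm difference has variance 2/30 times these values.

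| | r = 0.3 | r = 0.5 | r = 0.7 |
|---|---|---|---|
| Variance ratio, (1+r)/2 | 0.65 | 0.75 | 0.85 |
| Variance ratio with slope cost | 0.66 | 0.76 | 0.87 |
| 95% CI half-width, change (SD) | 0.61 | 0.52 | 0.40 |
| 95% CI half-width, ANCOVA (SD) | 0.50 | 0.45 | 0.37 |
| Power for 0.6 SD, change | 0.49 | 0.63 | 0.84 |
| Power for 0.6 SD, ANCOVA | 0.66 | 0.74 | 0.89 |

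Before the slope cost, 30 per arm with ANCOVA is worth 30/0.65 = 46, 30/0.75 = 40 and 30/0.85 = 35 per arm with change scores. Simulation of normal data gave the same variance ratios to within about 0.01, with type I error near 5% for both methods.

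*Baseline imbalance.* One standard error is √(2/30) = 0.26 SD. It moves the change-score estimate by (1−r)·0.26 = 0.18, 0.13 and 0.08 SD.

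*Unequal SDs.* If the follow-up SD is k times the baseline SD, the ratio is k²(1−r²)/(1 + k² − 2rk). At r = 0.5 this is 0.48/0.84 = 0.57 for k = 0.8, and 1.17/1.31 = 0.89 for k = 1.25.

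**Counts.** The documents give no rates, so every input is assumed: Poisson counts with log-normal subject rates; PNES median 8 per month, log SD 1.3; ED median 1 per 3 months, log SD 0.9; a 30% fall in both arms; a rate ratio of 0.5 for motivational interviewing; 3,000 trials per setting.

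| Power | Lower correlation | Middle | Higher |
|---|---|---|---|
| PNES (Spearman 0.3, 0.5, 0.7): Wilcoxon on change | 0.21 | 0.25 | 0.36 |
| PNES: rank ANCOVA | 0.46 | 0.52 | 0.68 |
| ED (Spearman 0.13, 0.22, 0.33): Wilcoxon on change | 0.17 | 0.18 | 0.20 |
| ED: rank ANCOVA | 0.35 | 0.36 | 0.37 |

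Type I error was 0.042–0.053 for both methods (4,000 null trials per setting). In 12 further PNES settings (median 4 or 20, log SD 0.8 or 1.3, three correlations), Wilcoxon on absolute change had power 0.17–0.68 and rank ANCOVA 0.40–0.98; rank ANCOVA was higher in all 12. If the PNES decrease means percent change, Wilcoxon gives 0.36, 0.44 and 0.63 in the main setting. That is closer, but still below rank ANCOVA.

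**Yes/no outcomes.** By exact enumeration at 25% vs. 60% with 30 per arm, the uncorrected chi-square, the t-test and Wilcoxon on 0/1 data each have power 0.802. Fisher's exact test has 0.719.

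**The case against.** The strongest reply is that nothing here is invalid: the planned tests hold their size, the outcomes are secondary, and the trial was not powered for them. All of that is true. This is avoidable imprecision, not bias.

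The second reply is that the 4-month follow-up paragraph can be read as comparing levels rather than changes, and that much of the apparent gain then comes from not subtracting. For ED visits this is right. On the same assumed rates, unadjusted Wilcoxon on the 4-month value has power 0.36, 0.36 and 0.35, against 0.35, 0.37 and 0.37 for rank ANCOVA, so adjustment adds almost nothing. For PNES frequency the level comparison has 0.44 throughout, against 0.47, 0.53 and 0.64. For QOLIE-10 at r = 0.3 it is 0.63 against 0.66, and the gain grows with r because the large-sample variance ratio to levels is 1−r² = 0.91, 0.75 and 0.51. The analysis section specifies change, however, so change is the proper comparator, and adjustment matches or beats the alternative on either reading.

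Third, every size depends on assumptions. With a rate ratio of 0.7, PNES power is 0.10–0.15 on change and 0.16–0.23 with rank ANCOVA, inadequate either way. All figures assume 30 complete patients per arm, although the plan foresees unreached and dropped patients. The gain in QOLIE-10 fades as r approaches 1 (ratio 0.97 at r = 0.9).

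Fourth, rank ANCOVA yields no between-arm estimate on the count scale. That is a fair limitation, and the reason to report medians and IQRs alongside the test.

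**Conclusion.** The point holds, as a recommended improvement. Baseline adjustment cuts the QOLIE-10 variance by 34%, 24% and 13% at r = 0.3, 0.5 and 0.7, assuming equal SDs and linearity. For skewed counts the advantage over absolute change is larger under the assumed inputs, but for ED visits it comes almost wholly from dropping the subtraction. The direction is firm; the size is not, because the documents give no correlation, SD, event rate or expected effect for these outcomes. The baseline instrument is described only as quality of life, but a change in QOLIE-10 already requires a baseline QOLIE-10. The primary outcome and its power are not affected.

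**What to change.** In B) Outcome data, replace the general test sentence for these three outcomes:

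- **QOLIE-10:** ANCOVA of the 4-month score on arm and baseline score, reporting the adjusted difference with 95% CI.
- **PNES frequency and ED visits:** rank ANCOVA (rank of the 4-month value on arm and rank of the baseline value), with medians and IQRs by arm at both times.
- **Test selection:** remove the normality-dependent choice for these outcomes.
- **Recall window:** state one window for 4-month seizure frequency, the same in both paragraphs.

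As a clarification only: once the two definitions of the primary outcome agree, state that yes/no outcomes use the uncorrected chi-square test, with risk difference and 95% CI. This keeps the power at 0.80; Fisher's exact test would lower it to 0.72.

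The cost is wording in one paragraph, plus the matching recall window in the follow-up paragraph. Statistically, adjustment uses one degree of freedom, about 1.8% of variance at 60 patients, already counted in the figures above. No new data, visits or patients are needed.
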